## **List of Abbreviations**

SEMS; Self Expanding Metal Stents

ERCP; Endoscopic Retrograde Cholangiopancreatogram

CBC; Complete Blood Count

CMP; Comprehensive Metabolic Panel

INR; International Normalized Ratio

1 Study Summary

Title	Preoperative Endoscopic Biliary Drainage with Self Expanding Metal Stents (SEMS) vs. Direct Surgical Resection for Patients with Severe Obstructive Jaundice
Short Title	Pre-surgery biliary stent placement vs. direct surgery in patient with obstructive jaundice
Protocol Number	
Phase	N/A
Methodology/Study Design	Randomized control trial
Study Duration	24 months
Study Center(s)	Thomas Jefferson University
Objectives	Investigate the advantage of using biliary SEMS in patients with severe jaundice prior to surgical resection
Number of Subjects	100
Diagnosis and Main Inclusion Criteria	Patients with periampullary cancer with profound jaundice
Study Therapy, Dose, Route, Regimen	Pre-operative SEMS placement vs direct surgical resection
Duration of administration and follow-up	Patient outcome data will be monitored at 30 days and 90 days post resection surgery.
Reference therapy	Direct surgery without stent placement
Statistical Methodology	This is a superiority trial of early surgery without biliary stenting, as compared with preoperative biliary drainage in patients with severe obstructive jaundice
Schema	<pre> graph LR     A[100 patients] --> B[50 patients with preoperative stent placement]     A --> C[50 patients without preoperative stent placement]     B --> D[Grade III or higher complication]     B --> E[No complications]     C --> F[Grade III or higher complication]     C --> G[No complications]   </pre>

3        **1.0 INTRODUCTION**

4        Pancreatic cancer is the second most common digestive cancer and fourth leading cause of cancer  
5        death in the United States for both men and women. Pancreatic tumors arising in the peri-  
6        ampullary region present with biliary obstruction in 64-77% of cases. Preoperative biliary  
7        decompression has been advocated in an attempt to reduce postoperative complications following  
8        attempted curative-intent surgery.

9  
10      This document is a protocol for a human research study. This study is to be conducted according  
11      to US and international standards of Good Clinical Practice (FDA Title 21 part 312 and  
12      International Conference on Harmonization guidelines), applicable government regulations and  
13      Institutional research policies and procedures.

14        **1.1 Specific Aims and Hypothesis**

15        The primary aim of this study is to compare the 30 and 90-day overall/cumulative grade III or  
16        higher complication rates between patients with severe obstructive jaundice undergoing  
17        preoperative endoscopic biliary drainage with SEMS and patients undergoing direct surgical  
18        resection. In this study, **One arm undergoes preoperative biliary drainage followed by surgery and**  
19        **the other arm undergoes surgical resection** without prior biliary drainage. Secondary aims will be  
20        to compare surgical outcomes including mortality, intra-operative parameters, hospital length of  
21        stay, ICU length of stay, readmission rate and time to commencement of adjuvant treatment.

22        **1.2 Background and Rationale**

23        Despite the fact that endoscopic and percutaneous placement of biliary stents is technically  
24        successful in 90-95% of cases, routine preoperative biliary drainage for pancreatic cancer remains  
25        controversial.[4, 5] Pooled data from retrospective studies published over the past several years  
26        have shown similar rates of 30-day mortality after pancreaticoduodenectomy in those who have  
27        undergone biliary decompression as compared to those who have not. A few studies have  
28        suggested that routine preoperative drainage in patients undergoing surgery for cancer of the  
29        pancreatic head may increase overall complications, likely due to complication related to the  
30        endoscopy itself (i.e. pancreatitis, bleeding, perforation) and complications related to stent  
31        failure.[6] In the largest, multicenter, randomized trial to date, patients were randomly assigned  
32        to undergo either endoscopic preoperative biliary drainage for 4 to 6 weeks, followed by surgery,  
33        or surgery alone after diagnosis. In this study, endoscopic preoperative biliary drainage did not  
34        have a beneficial effect on the surgical outcome but rather was associated with an increase in  
35        serious complications.[7]

36  
37        On the other hand, outcome measures have not been standardized and the lack of complete data  
38        on surgical complications following preoperative drainage make direct comparisons difficult and  
39        potentially biased. Many of the prior studies used plastic stents for preoperative decompression,  
40        which when compared to self-expanding metal stents (SEMS) result in greater rates of re-  
41        intervention and cholangitis. A recent meta-analysis of 1989 patients showed that SEMS have  
42        higher stent insertion success, lower risk of stent occlusion, lower re-intervention rate, fewer  
43        therapeutic failures, and fewer episodes of cholangitis compared to plastic stents making them the  
44        optimal choice for biliary decompression.[8] Also a recent randomized controlled trial confirmed  
45        that SEMS are superior to plastic stents with regard to functional stent time and showed that the  
46        total health care cost is similar for placing SEMS or plastic stents even in patients with survival  
47        less than 3 months.[9] Thus, this study will provide unique perspective on the potential  
48        advantages of biliary decompression using SEMS. Additionally, prior studies have excluded  
49        severely jaundiced patients (serum bilirubin > 14.6), a population that may have derived the

50 greatest benefit from preoperative drainage, since these patients are more likely to have impaired  
51 liver function. In fact, patients with malignant obstruction who present with severe jaundice  
52 ( $>10\text{mg/dL}$ ) are likely at higher risk for poor outcome following surgery.[10] These patients may  
53 also benefit from preoperative drainage to alleviate pruritus and correct coagulation  
54 disturbances.[11] Thus, although preoperative biliary drainage may not be routinely  
55 recommended for all patients with malignant biliary obstruction, drainage may be potentially  
56 advantageous for those patients with severe jaundice using a SEMS.

57 **1.3 Study Therapy**

58 Both preoperative SEMS placement and direct surgical resection are considered acceptable  
59 standard of care in this patient population.

60  
61 SEMS (Wallflex, Boston Scientific) will be used. The WallFlex Biliary Stent System is FDA-  
62 cleared in the US, and is indicated for use in the palliative treatment of biliary strictures produced  
63 by malignant neoplasms. Also, the WallFlex Biliary RX Stent is 510(k) cleared for the treatment  
64 of biliary strictures produced by malignant neoplasms and relief of malignant biliary  
65 obstruction prior to surgery. This represents the first biliary metal stent with labeling to support  
66 pre-operative drainage in the US.

67 **1.4 Preclinical Data**

68 Please see clinical data below

69 **1.5 Clinical Data to Date**

70 A recent meta-analysis of 1989 patients showed that SEMS have higher stent insertion success,  
71 lower risk of stent occlusion, lower re-intervention rate, fewer therapeutic failures, and fewer  
72 episodes of cholangitis compared to plastic stents making them the optimal choice for biliary  
73 decompression.[8] Also a recent randomized controlled trial confirmed that SEMS are superior to  
74 plastic stents with regard to functional stent time and showed that the total health care cost is  
75 similar for placing SEMS or plastic stents even in patients with survival less than 3 months

76 **1.6 Dose Rationale and Risk/Benefits**

77 The study doesn't involve drug administration.

78 **2.0 STUDY OBJECTIVES**

79 **2.1 Primary Objective:**

80 The primary aim of this study is to compare the 30 and 90-day overall complication rates between  
81 patients with severe obstructive jaundice undergoing preoperative endoscopic biliary drainage  
82 with SEMS and patients undergoing direct surgical resection.

83 **2.2 Secondary Objective:**

84 Secondary aims will be to compare surgical outcomes including hospital length of stay, ICU  
85 length of stay, readmission rate, disposition from hospital, emergency room visits, urgent care  
86 center visits and time to commencement of adjuvant treatment.

87 **3.0 STUDY DESIGN**

88 **3.1 General Design**

89 This is a Randomized controlled trial.

92 ERCP will be performed on those who are randomized to the intervention group with 24 hours of  
93 randomization. The patient will be followed at 30 days and 90 days post-operatively.

94 **3.2 Primary Study Endpoints**

95 30 and 90 day- complication rates between patients with severe obstructive jaundice undergoing  
96 preoperative endoscopic biliary drainage with SEMS and patients undergoing direct surgical  
97 resection

98 **3.3 Secondary Study Endpoints**

99 Secondary aims include the total number of complications, intraoperative estimated blood loss,  
100 number of required fluid boluses, postoperative hospital LOS, readmission rate, disposition from  
101 hospital, time to commencement of adjuvant treatment, emergency room visits, urgent care center  
102 visits, and perioperative mortality. Complications will include pancreatic fistula, delayed gastric  
103 emptying, intra-abdominal abscess, cardiac complications, respiratory complications, deep vein  
104 thrombosis, pulmonary embolism, urinary tract infection, wound infection, acute renal failure,  
105 hemorrhage, hepaticojjunostomy leak, and duodenojjunostomy leak. Pancreatic fistula was  
106 defined and graded according to the International Study Group of Pancreatic Fistula criteria.  
107 Delayed gastric emptying was defined and graded according to the International Study Group of  
108 Pancreatic Surgery. Wound infections and urinary tract infection were defined according to the  
109 Centers for Disease Control and Prevention guidelines. Cardiac complications were defined  
110 according to the American College of Cardiology and renal complications were defined by the  
111 Acute Dialysis Quality Initiative.

112 **3.4 Primary Safety Endpoints**

113 Both SEMS placement and direct surgical resection are considered acceptable standard of care  
114 practices.

115 **4.0 SUBJECT SELECTION AND WITHDRAWAL**

116 **4.1 Inclusion Criteria**

117 -Adult patients age >18 regardless of gender or ethnicity  
118 -Patients with peri-ampullary pancreatic cancer.  
119 -Patients with serum bilirubin greater than 10mg/dL  
120 -Adequate birth control

121 **4.2 Exclusion Criteria**

122 -Patients with evidence of distant metastasis on CT or MRI  
123 -Patients anticipated to require vascular reconstruction  
124 -Patients with cholangitis  
125 -Patients who previously underwent biliary decompression for cholangitis by ERCP or PTC  
126 -Patients with low performance score (Karnofsky performance status scale < 50)  
127 -Patients with known preexisting liver disease with associated elevated bilirubin  
128 -Patients who are pregnant or actively breast feeding.

129 **4.3 Gender/Minority/Pediatric Inclusion for Research**

130 Any patient can be included if older than 18 years of age irrespective of gender, color, or  
131 ethnicity.

133 4.4 Subject Recruitment and Screening

134 One Hundred patients older than 18 years with periampullary cancer presenting with jaundice and  
135 total bilirubin greater than 10mg/dL will be included in the study.

136 Patients will be recruited from clinic (gastroenterology and pancreaticobiliary surgery) or when  
137 admitted to the hospital for workup and/or management and will be consented at that time.

138

139 4.5 Early Withdrawal of Subjects

140 **4.5.1 When and How to Withdraw Subjects**

141 Patients can withdraw from the study at any time. Stent placement is the standard of care and thus  
142 subjects who elect to withdraw from the study will continue to have the biliary stent in place and  
143 be followed regularly similar to patients that are enrolled in the study.

144 **4.5.2 Data Collection and Follow-up for Withdrawn Subjects**

145 Subjects who elect to withdraw from the study will continue to be followed on a regular basis.  
146 Data that is important to the integrity of the final study analysis and the safety profile of the  
147 SEMS will be collected after obtaining approval of the subjects.

148

149 **5.0 STUDY DRUG/THERAPY**

150 5.1 Description

151 The stents to be used in this study are FDA approved WallFlex Biliary RX Stents (Boston  
152 Scientific Corporation, Natick, MA, USA) which are available in diameters of 8 or 10 mm and  
153 lengths of 40, 60, and 80 mm.

154 5.2 Treatment Regimen

155 Stent to be placed pre-operatively in the intervention group to be removed during surgery.

156 5.3 Risks

• Pain	• Infection	• Tumor overgrowth around ends of stent
• Bleeding	• Inflammation	• Mucosal hyperplasia
• Fever	• Recurrent obstructive jaundice 26% (likely)	• Cholangitis
• Nausea	• Stent occlusion	• Cholecystitis 10% (likely)
• Vomiting	• Tumor ingrowth through the stent	• Pancreatitis 6% (possible)
• Bile duct ulceration	• Perforation of duodenum or bile duct	• Stent migration 8% (possible)
• Perforation of the gall bladder due to the stent covering the cystic duct	• Stent misplacement	

157

158

159 Once again, placement of SEMS is the standard of care for patient with profound jaundice despite  
160 the lack of evidence to support this practice.

161 5.4 Method for Assigning Subjects to Treatment Groups  
162 A randomization schedule will be created by the study statistician using the method of random  
163 permuted blocks. Randomization assignments will be loaded into a REDCap database before  
164 study enrollment begins. Randomization assignments will be accessed through the REDCap  
165 randomization facility.

166 5.5 Preparation and Administration of Study Drug/Therapy  
167 The intervention group will receive a WallFlex Biliary RX Stents (Boston Scientific Corporation,  
168 Natick, MA, USA)

169 5.6 Subject Compliance Monitoring  
170 The stent will placed by ERCP and won't be removed before surgery unless indicated. Follow up  
171 phone calls to ascertain secondary endpoints will be made at 30 and 90 days.

172 5.7 Prior and Concomitant Therapy  
173 Subject in the study are to continue any medications that they are on. Those who are randomized  
174 to the intervention group may be asked to hold antiplatelet/anticoagulation agents prior to the  
175 ERCP in coordination with their prescribing doctor.

176 5.8 Blinding of Study Drug  
177 Unblinded study

178 **6.0 STUDY PROCEDURES**

179

180 **6.1 Study Visit Schedule**

181 **Screening:**  
182 Patients will be screened in clinic or if admitted as inpatients. Patient must satisfy the inclusion  
183 criteria listed above. Patient must carry a diagnosis of per-ampullary cancer. Basic labs will be  
184 withdrawn including CBC, CMP and INR.

185

186 **Randomization**  
187 **Peri-operative:** The patient will be admitted and labs will obtained including CBC, CMP and  
188 INR prior to surgery.

189

190 **Post-operative:**  
191 Visit 1: This will be scheduled 3-4 weeks after hospital discharge. Labs and imaging may be  
192 ordered by the surgeon if needed.

193 Follow-up  
194 Patients will be followed up to 90 days after the surgery. A phone call will be placed to the  
195 patient by research staff to ascertain secondary endpoints. Jefferson EMR will be accessed  
196 to ascertain primary endpoint data.

197

198 **7.0 STATISTICAL PLAN**

199 7.1 Sample Size Determination  
200 Based on previous data, we assumed an overall grade III or higher complication rate of  
201 50% in the control group. Although we are unsure of the expected rate in the pre-operative  
202 biliary stenting group, a 30% or greater reduction in the grade III or higher complication

would be meaningful. The sample size will be 100 subjects (50 per arm). We calculated power under various alternatives for the biliary stenting group complication rate using a two-group large-sample normal approximation test of proportions, with a one-sided significance level of 0.05, to test the null hypothesis that the grade III or higher complication rate in surgery with biliary stenting is greater than or equal to the control rate (50%). We have 84% power to detect a reduction if the true rate with biliary stenting is 25%, 66% power if the true rate is 30%, and 44% power if the true rate is 35%.

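### The primary endpoint does not say when its 30- and 90-day windows start; counted from surgery, as the timing statements suggest, it leaves out grade III or higher complications before surgery

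*Combined protocol and SAP*

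**What the plan says.** **The endpoint and rule name no origin.** Section 1.1 says "The primary aim of this study is to compare the 30 and 90-day overall/cumulative grade III or" higher complication rates, section 2.1 says "The primary aim of this study is to compare the 30 and 90-day overall complication rates between" the arms, and section 3.2 says "30 and 90 day- complication rates between patients with severe obstructive jaundice undergoing" the two strategies. Section 7.2 estimates the rates separately at 30 and 90 days. It calls stenting effective if the upper one-sided 95% bound for stent minus control is below zero at both times. None of the four says day 30 or day 90 after what.

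**Outcome timing elsewhere points to surgery.** The Study Summary has "Patient outcome data will be monitored at 30 days and 90 days post resection surgery". Section 3.1 has "The patient will be followed at 30 days and 90 days post-operatively". Section 6.1 has "Patients will be followed up to 90 days after the surgery", and the same paragraph contains the only sentence on how primary endpoint data are obtained. The interim rule in 8.4 looks at post-operative mortality or morbidity.

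**Two items point towards randomisation.** One is the word cumulative in 1.1. The other is the adverse event period in 8.1, which runs from randomisation to 90 days after surgery. Neither is linked to the 7.2 rule.

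**Treatment before surgery differs by arm.** Section 3.1 states: "ERCP will be performed on those who are randomized to the intervention group with 24 hours of" randomisation. Section 1.2 reports that a few studies suggest routine drainage may raise overall complications, likely through those of "endoscopy itself (i.e. pancreatitis, bleeding, perforation) and complications related to stent" failure.

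**Population.** Section 7.3 analyses all randomised patients as randomised. It does not say how a patient who never has an operation is scored.

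**The concern.** Section 1.1 describes the stent arm as a strategy: drainage, then surgery. If day 0 is the operation, any serious harm from the first half of that strategy falls outside the primary comparison. Controls have no protocol procedure in the same interval. The trial could then report that stenting lowers grade III or higher complications when patients, followed from the point of allocation, fare no better.

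A patient who is never operated on has no post-operative window at all. Because 7.3 keeps such patients in the analysis, someone must decide how to score them, and in an unblinded study (5.8) that decision is best made in advance.

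**Working it through.** **1. The plan's own power.** Inputs from 7.1: 50 per arm, control rate 0.50, one-sided 0.05, stent rate p of 0.25, 0.30 or 0.35. With m = (0.50 + p)/2,

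power = Φ{[(0.50 − p) − 1.645·√(2m(1 − m)/50)] / √[(0.25 + p(1 − p))/50]}.

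For p = 0.25: m = 0.375, and (0.25 − 1.645 × 0.0968)/0.0935 = 0.97, so power is 83.4%. The other two give 65.7% and 44.9%. The plan states 84%, 66% and 44%, so its figures reproduce. Section 7.1 does not say whether these rates are totals from randomisation or post-operative rates.

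**2. What the 7.2 rule does if pre-operative events are not counted.** Assumptions, none of them from the documents except the 50% and the 50 per arm:
- the true total from randomisation is 50% in both arms;
- a share q of the stent arm has a grade III or higher event before surgery, and no control does;
- a share r of the counted 90-day events occurs by day 30.

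Two models for the counted stent rate:
- Independent (pre-operative events independent of later ones): 1 − 0.50/(1 − q), which is 0.474 at q = 5% and 0.444 at q = 10%.
- Only event (the pre-operative event is the patient's only one): 0.50 − q, which is 0.45 and 0.40.

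Success at one time means d + 1.645·√{[s(1 − s) + c(1 − c)]/50} < 0, where s and c are the observed stent and control proportions and d = s − c. The 90-day counts are binomial. Each 30-day count is binomial given its 90-day count, with probability r. Exact enumeration gives the chance of declaring stenting effective:

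| q | Independent, r = 90% | Only event, r = 90% | Independent, r = 70% | Only event, r = 70% |
|---|---|---|---|---|
| 0% | 3.0% | 3.0% | 2.1% | 2.1% |
| 5% | 5.3% | 8.5% | 3.7% | 5.9% |
| 10% | 9.4% | 19.5% | 6.6% | 13.6% |

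At a single time point, which is not the 7.2 rule, the figures for q = 5% and 10% are 7.7% and 13.0% (independent), or 11.9% and 25.4% (only event).

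**3. If controls also have uncounted events** (both-times rule, r = 90%; independent, then only event):
- 5% in each arm: 3.2% and 3.3%.
- 10% in each arm: 3.4% and 3.7%.
- Stent 5%, control 10%: 1.7% and 1.1%.
- Stent 10%, control 5%: 5.9% and 9.4%.

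The excess appears only when the stent arm has more uncounted events than control.

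**4. Patients never operated on** (illustration at one time point). Suppose 5 of 50 stent patients and no controls are never operated on, with rates of 30% and 50% among those who are. The upper bound is:
- −0.074 if the five are scored event-free (stent rate 0.30 × 45/50 = 0.27);
- −0.038 if they are excluded;
- +0.032 if they are scored as events (stent rate (0.30 × 45 + 5)/50 = 0.37).

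The verdict turns on a rule that is not written down.

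**The case against.** The strongest reply is that the plan does have a clock. Every statement on outcome timing gives surgery, and the randomisation start in 8.1 is a safety-reporting period. Section 1.0 speaks of reducing postoperative complications, and the list in 3.3 is mainly surgical. A post-operative endpoint may therefore be intended, and for that question a lower post-operative rate is a real difference. This stands in part. A reader might infer that the endpoint has no usable reading and the analysis cannot be run; the documents do not support that. What remains is that the endpoint and rule do not adopt the surgery clock, while 1.1 frames the comparison as cumulative and the stent arm as a whole strategy.

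A second reply is that the harm is assumed. The risks in 5.3 carry no grade or timing, and no interval to surgery is given for either arm; the 4 to 6 weeks in 1.2 belong to a cited trial. Many earlier studies used plastic stents, and 1.2 says metal stents do better on occlusion, re-intervention and cholangitis. Undrained controls may also have events while waiting. All of this stands. It means that a firm claim of bias towards stenting is not supported. The endoscopy part of the risk does carry over to metal stents.

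Third, pre-operative events are reported under 8.1 and reviewed by the Medical Monitor and the monitoring committee. They would be visible, but outside the 7.2 rule.

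A reader might also infer that every unresected patient lacks a day 0. That goes too far: 3.1 and 6.1 anchor to the operation, so a patient explored but not resected has a date. The gap concerns patients never operated on.

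**Conclusion.** The point holds as a should-fix. The primary endpoint and the 7.2 rule need a stated time zero. On the surgery clock that the timing statements suggest, grade III or higher events between randomisation and surgery are left out, including ERCP and stent complications.

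With a true total of 50% in both arms, none uncounted in controls and 90% of events by day 30, the rule declares stenting effective in 5.3% to 8.5% of trials when 5% of the stent arm is affected, and in 9.4% to 19.5% when 10% is. The lower figure takes pre-operative events as independent of later ones; the upper takes them as the patient's only event. With similar or more such events in controls, the chance was 3.7% or less in the cases tried. These calls are wrong only for the total from randomisation.

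It would be tempting to quote 12% to 25% as the rule's error rate. Those figures apply to one time point under the only-event model, whereas 7.2 requires success at both. The severity does not rest on a known size of bias. It rests on the endpoint leaving out part of the strategy under test, when the needed events are already reported.

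**What to change.** - In 3.2 and 7.2, with 1.1 and 2.1 aligned, define the primary endpoint as the proportion of all randomised patients with at least one grade III or higher complication counted from randomisation. The window can run through 30 and 90 days after surgery, as in 8.1, or over a fixed period from randomisation that gives both arms equal time at risk.
- State that ERCP and stent complications count.
- State one rule, the same in both arms, for the window and scoring of patients never operated on. Add a sensitivity analysis with all of them event-free and all of them as events.
- Report post-operative-only rates as secondary.
- In 7.1, say whether the 50% and the 25%, 30% and 35% are totals from randomisation, or restate power.

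**Cost.** Mostly wording. Pre-operative adverse events are already reportable under 8.1, but they must be graded on the scale used for the endpoint; the form in 8.2 records only mild, moderate or severe.

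**Downsides.** A window that ends relative to surgery gives more time at risk to the arm that waits longer. Power for a given post-operative reduction also falls. With a post-operative stent rate of 25% and independent pre-operative events, the total is 1 − 0.75(1 − q): 0.25, 0.2875 and 0.325 at q = 0%, 5% and 10%. Against 0.50 at one time point, exact power is 85%, 72% and 56%.

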#### Serious Adverse Event

Adverse events are classified as serious or non-serious.

A **serious adverse event** is any AE that is:

- fatal

247           • life-threatening  
248           • requires or prolongs hospital stay  
249           • results in persistent or significant disability or incapacity  
250           • a congenital anomaly or birth defect  
251           • an important medical event

252  
253           Important medical events are those that may not be immediately life threatening, but are  
254           clearly of major clinical significance. They may jeopardize the subject, and may require  
255           intervention to prevent one of the other serious outcomes noted above. For example, drug  
256           overdose or abuse, a seizure that did not result in in-patient hospitalization or intensive  
257           treatment of bronchospasm in an emergency department would typically be considered  
258           serious.

259  
260           All adverse events that do not meet any of the criteria for serious should be regarded as  
261           ***non-serious adverse events.***

262           Adverse Event Reporting Period

263           The study period during which adverse events must be reported is normally defined as the  
264           period from the initiation of any study procedures to the end of the study treatment follow-  
265           up. For this study, the study treatment follow-up starts at randomization and ends at 90  
266           days after the surgery.

267           Preexisting Condition

268           A preexisting condition is one that is present at the start of the study. A preexisting  
269           condition should be recorded as an adverse event if the frequency, intensity, or the  
270           character of the condition worsens during the study period.

271           General Physical Examination Findings

272           At screening, any clinically significant abnormality should be recorded as a preexisting  
273           condition. At the end of the study, any new clinically significant findings/abnormalities  
274           that meet the definition of an adverse event must also be recorded and documented as an  
275           adverse event.

276           Post-study Adverse Event

277           All unresolved adverse events should be followed by the investigator until the events are  
278           resolved, the subject is lost to follow-up, or the adverse event is otherwise explained. At  

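### Length of stay is post-operative in section 3.3 but unrestricted in 1.1 and 2.2; the 3.3 version omits pre-surgery hospital days, is undefined without surgery, and has no rule for death

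*Combined protocol and SAP*

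**What the plan says.** Three sections describe the stay endpoint, and they differ.

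- Section 1.1 (aims): "to compare surgical outcomes including mortality, intra-operative parameters, hospital length of" stay. No limit to the post-operative period.
- Section 2.2 (secondary objective): "Secondary aims will be to compare surgical outcomes including hospital length of stay, ICU" stay. Again no limit.
- Section 3.3 (secondary endpoints): "number of required fluid boluses, postoperative hospital LOS, readmission rate, disposition from" hospital. Here only the post-operative stay counts. ICU stay, named in 1.1 and 2.2, is absent. Readmission has no index discharge and no start date in any of the three sections.

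On what happens before surgery, section 3.1 says "ERCP will be performed on those who are randomized to the intervention group with 24 hours of" randomisation, and sections 5.2 and 5.6 keep the stent in until surgery unless removal is indicated. Section 4.4 allows recruitment of patients already "admitted to the hospital for workup and/or management and will be consented at that time", and the peri-operative step in section 6.1, not limited to one arm, says "The patient will be admitted and labs will obtained including CBC, CMP and" INR before surgery.

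On analysis, section 7.2 gives continuous outcomes a t-test or Wilcoxon test and time-to-event outcomes Kaplan-Meier and log-rank methods. It does not say which applies to length of stay, or what to do with deaths. Section 7.3 analyses everyone randomised. Perioperative mortality is a separate secondary endpoint in 3.3.

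**The concern.** Randomisation assigns a strategy: stent then surgery, or surgery directly. A count that starts at surgery begins after part of one strategy has been delivered. Hospital days for the ERCP, or for a complication of the stent while the patient waits, fall outside it. The protocol expects such complications: section 1.2 discusses harm from endoscopy and stent failure, and section 5.3 lists, among others, "Recurrent obstructive jaundice 26% (likely").

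The adverse-event clock is set differently. Section 8.1 reads "up. For this study, the study treatment follow-up starts at randomization and ends at 90" days after surgery, so the plan already treats the pre-operative period as part of follow-up for safety.

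Two further gaps concern who has a value and what it means. A patient who is randomised but never operated on has no post-operative stay. A patient who dies soon after surgery has a short one, which a rank or mean comparison reads as a good result. At stake is how far the secondary comparison of hospital use between the two strategies can be trusted.

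**Working it through.** **The plan's own figures.** No mean, SD, death rate or power is given for length of stay. The only computed figures are in section 7.1, for the complication endpoint: 84%, 66% and 44% power at stent-arm rates of 25%, 30% and 35%. With 50 per arm, control rate 0.50 and one-sided 0.05, power = Φ((d − 1.645·SE0)/SE1), where d = 0.50 − p, SE0 = √(2·p̄(1−p̄)/50) and SE1 = √(0.25/50 + p(1−p)/50). At p = 0.25: p̄ = 0.375, SE0 = 0.0968, SE1 = 0.0935, so (0.25 − 0.1593)/0.0935 = 0.970 and power is 83.4%. The other two give 65.7% and 44.9%. The figures reproduce to within a point, and they have no bearing on length of stay.

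**Omitted days.** Let the mean post-operative stay be equal in the two arms, and let stented patients spend k hospital days between randomisation and surgery and controls c days. The 3.3 endpoint then shows a difference of 0, and the true difference in total stay is k − c. If k − c is 1 to 5 days (assumed), 1 to 5 days go unseen. If k − c is zero, nothing is hidden; if it is negative, the omission works against stenting. The documents give neither k nor c, nor the interval from stent to surgery.

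**Deaths, effect on the mean.** Assume post-operative stay is lognormal with median 10 days and log-SD 0.5, so the mean is about 11.3 days. If a share m of an arm dies in hospital on day t, the arm's mean moves by m·(t − 11.3).

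| Share dying | Death on day 3 | Death on day 30 |
|---|---|---|
| 2% | −0.17 | +0.37 |
| 5% | −0.42 | +0.93 |
| 10% | −0.83 | +1.87 |

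**Deaths, effect on the test.** On the same assumptions, with 50 per arm, stays otherwise equal and deaths by day 3 in one arm only, 4,000 trials were simulated per setting. A one-sided 0.05 Wilcoxon test favoured the arm with the deaths in 4.9% of trials with no deaths, 10.8% with 5% deaths and 21.8% with 10% deaths.

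**Patients without surgery.** Section 7.3 requires a value for everyone randomised. Post-operative stay is missing by definition for a patient who dies or is found unresectable before an operation, and no rule covers this. Hospital days from randomisation exist for every patient.

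**The case against.** The strongest reply is that sections 1.1 and 2.2 call these surgical outcomes, and that post-operative stay is a coherent measure of surgical recovery. That stands, and it is the reason to keep the measure. It does not settle which of the three wordings governs, and a measure of recovery among those operated on does not compare the strategies.

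Controls can lose pre-operative days too, through inpatient recruitment and admission before surgery. This also stands. The net imbalance is unknown, so a reader should not infer that the endpoint favours stenting by construction. No section says that ERCP needs an overnight stay.

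The omitted days are not lost to the study altogether: adverse events run from randomisation, and those that lead to hospitalisation are recorded as serious. This is true in part. Section 8.1 also exempts hospitalisation for elective procedures for a pre-existing condition, and for treatment of the target disease unless judged a worsening, so a routine ERCP stay might not appear. A safety listing does not correct the stay comparison in any case.

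Mortality is reported separately, so a death is not hidden. Agreed, but that does not repair a stay test in which the death counts as an early discharge.

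A reader might also infer that readmission is counted only after the surgical discharge. The documents do not say so; they simply leave the starting point open.

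**Conclusion.** The point holds as an inconsistency with a possible direction. Section 3.3 narrows the endpoint that 1.1 and 2.2 leave open. The narrowed version drops a period in which only one arm has a planned procedure, and it would favour stenting if that procedure or its complications cost more hospital days than controls spend before surgery. It is also undefined for patients not operated on, and there is no rule for death.

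The size cannot be derived from the documents. A reader might add the rates in section 5.3 (26% + 10% + 8% + 6% = 0.50 events per stented patient), assume that a third to all fall before surgery at 2 to 5 hospital days each, and reach 0.50 × 1/3 × 2 = 0.33 to 0.50 × 5 = 2.5 days. The documents do not support that range. The rates carry no time window and no link to admission, the events may overlap, the stent is removed at surgery, and both multipliers are assumed.

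Nor do the documents support the inference that death in hospital always shortens the stay. They are silent, and the table above shows that a late death lengthens it. The simulated percentages depend on early deaths confined to one arm and are illustrations only.

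This is a minor point on a secondary endpoint. The primary decision rule and the sample size do not change.

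**What to change.** 1. Reconcile sections 1.1, 2.2 and 3.3, and state whether ICU stay is an endpoint.
2. Make the between-arm comparison total hospital days (and ICU days) from randomisation, including any ERCP stay and pre-operative admissions, over one fixed window of equal length in both arms.
3. State the window length and check that it covers the drainage interval and post-operative recovery. The interval is not given for this trial. If it resembled the 4 to 6 weeks of the randomised trial described in 1.2 (an assumption), a 90-day window from randomisation would leave about 48 to 62 post-operative days in the stent arm (90 − 42 and 90 − 28), and full cover of 90 post-operative days would need about 118 to 132 days (28 + 90 and 42 + 90).
4. In 7.2, name the method for this endpoint and analyse it so that death is not counted as a short stay, for example as days alive and out of hospital.
5. Keep post-operative stay as a descriptive measure among those operated on.
6. Start the readmission count from a stated point that is the same in both arms.

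The cost is small but not nil. Sections 5.6 and 6.1 collect secondary endpoints by phone and reserve the EMR for the primary endpoint, so hospital dates would have to come from the EMR as well. Because follow-up now ends 90 days after surgery, record review would run somewhat longer in controls. Comparison with published post-operative stay becomes less direct, which item 5 largely offsets.
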